2.6 Study Duration

It is estimated that the study can be completed within 18 months and that data analysis and paper preparation can be completed in an additional six months.

2,7 Statistical Procedures and Sample Size Justification

2.7.1 Statistics

The primary PSG efficacy variables will be sleep efficiency and WASO computed as a mean of nights 7 and 8. The secondary PSG measures will include nocturnal sleep latencies and sleep stages. The primary daytime measures will be the MSLT scores from day 8 and the FWL test results (the average of the am and pm tests) from day 1 and day 8. Secondary daytime measures will include the in-lab self-ratings of sleepiness/fatigue and pain. Another set of secondary measures will be the morning ratings of sleep and previous day's pain collected on the internet administered questionnaires during each 9 day treatment condition. The in-lab sleep, daytime sleepiness/fatigue, and pain data for each dependent variable of the two 9 day conditions will be compared using two factor MANOVAs with drug (suvorexant vs placebo) and days (7 and 8) as the two repeated factors. The internet questionnaire data will be treated similarly using drug and days as two repeated measures. In addition we will conduct path

analyses to determine the degree to which the change in nociceptive sensitivity is mediated directly by suvorexant and indirectly by suvorexant's effect on sleep.

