2.4.2 Exclusion Criteria

- Pain symptoms (unrelated to fibromyalgia) that could interfere with the interpretation of outcome measures; regional pain syndromes (eg. back, neck); multiple surgeries; pain from a traumatic injury; a confirmed current or previous diagnosis of rheumatoid arthritis, or similar disorders, inflammatory arthritis, or other autoimmune disease, osteoarthritis, tendonitis, unstable medical or psychiatric disorders.
- Any condition that could confound assessment of sleep, including depression (scoring 14 > on the Hamilton Depression Rating Scale (HAM-D), anxiety (scoring 24> on the Hamilton Anxiety Rating Scale (HAM-A), other psychiatric disorders, chronic medical conditions (e.g. liver disease, heart failure) or uncontrolled medical conditions.
- Consuming >14 alcoholic beverages per week (and/or >5 or > 4 drinks per single occasion for males and females, respectively) and >300mg of caffeine per day.
- The inability to discontinue, hypnotics or antidepressants.
- Substance abuse within the last 2 years and/or a failed urine drug screen;
- Primary sleep disorders, including narcolepsy, or circadian rhythm sleep disorder, excluding insomnia;
- Respiratory disturbances [apnea hypopnea index] or periodic limb movement arousal index greater than 10 per hour of sleep.
- Having a history of frostbite and/or Raynaud's syndrome.
- Current pregnancy or breast-feeding.

While patients will be told to discontinue hypnotic use, they will be allowed use of pain medications throughout the study to be recorded in a daily diary, as long as they are using a stable dose on a regular basis. The one exception will be that sedating tricyclic antidepressant use will be excluded. Patients will be asked to discontinue their antidepressant or hypnotic use two weeks before entering the study protocol.

Those qualifying will receive suvorexant 20 mg and placebo for each of 9 nights in a cross over design with 7 nights of washout between treatments. PSGs will be collected on nights 7 and 8 of each crossover treatment arm. During day 8 of each treatment a MSLT (1000, 1200, 1400, and 1600 hr) will be done, and on days 1 and 8 nociceptive sensitivity [finger withdrawal latency (FWL)] testing to a radiant heat stimulus (1100 and 1500 hr) will be conducted. On days 1 and 8 self-reported mood and pain indices will also be completed prior to each nociceptive sensitivity test.

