2.5.2 Daytime Sleepiness/Alertness (MSLT)

Each test of the MSLT will be conducted according to the standard research MSLT protocol (20). Participants will be placed in bed in quiet, darkened rooms and instructed to close their eyes, relax, and fall asleep. Each test is concluded after 20 minutes of continuous wake or after three continuous 30s epochs of stage one sleep, or one epoch of any other sleep stage. Latency to sleep onset will be scored as min to the first epoch of sleep or 20 min if sleep did not occur. The latencies for the 4 tests are averaged to generate a single latency value.

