2.5.3 Nociceptive Sensitivity (FWL)

A radiant heat method will be used to assess nociceptive sensitivity (21). Participants are seated in a comfortable chair at a desk with their hand resting on top of a metal box housing the heat source. The pad of the index finger (fingerprint whorl) is centered over a 3-mm hole

through which the heat radiates. The heat source is a 100-watt projection bulb, located 10 mm from the finger. A potentiometer controls the amount of current delivered to the light bulb, thereby varying heat intensity. On each trial, participants are instructed to place their index finger on the hole through which the heat source radiates and to withdraw their index finger when they first began to feel pain. Once finger withdrawal occurs, a photocell (mounted on a post located above the finger) detects the light (from the bulb underneath) and stops a digital timer connected to the circuit. Both index fingers are tested and the heat intensities are adjusted on each trial such that five different heat intensities (ranging from 83.4 to 101.6 degrees Fahrenheit, measured at steady-state after 10-sec duration) are presented in a randomized order. The FWL from left and right index fingers are averaged. The primary dependent measure is mean FWL (to a resolution of 0.01 sec) for each of the 5 heat intensities.

Patients initially will undergo a training session to familiarize themselves with the nociceptive testing equipment and procedures. The threshold at which a finger withdrawal response is elicited for each participant is established. The threshold radiant heat intensity is defined as the intensity that produces FWL of <21 sec.

As to the validity of the radiant heat method, our studies have shown FWL is systematically related to stimulus intensity (greater intensity = shorter FWL), basal level of sleepiness/alertness (greater sleepiness = shorter FWL), and codeine versus placebo (codeine = longer FWL) (21). Importantly, in healthy normals without sleep disturbance reducing sleep time by as little as 2 hrs reduces FWL and increasing sleep time by as little as 1 hr increases FWL (22,23). Further, in patients with moderate to severe obstructive sleep apnea (OSA) treated with Continuous Positive Airway Pressure (CPAP), thereby eliminating the OSA and consolidating sleep, FWL is increased and when the CPAP is discontinued for two nights FWL is again reduced (24).

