2.5.5 Safety Monitoring

Each participant will complete the Columbia Suicidality Scale at screening and on study day 1 and 8. Additionally the Hamilton Depression Rating Scale (HAM-D) and Hamilton Anxiety Rating Scale (HAM-A) will also be completed on those days. The rating scales will be administered between the first and second nociceptive sensitivity testing (at approximately 1130 hr) on each day. Changes on any of these scales from the scores established at the baseline will be reported as AEs (see below). On day three of each of the treatment periods the patient/subjects will be contacted by phone to determine whether they are experiencing AEs.

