2.7.2 Sample Size

Our estimates of necessary sample size and the associated powers are presented in Appendix A. The sample sizes and associated powers are presented for each of the primary outcome measures. Given these assessments, we have chosen to recruit 30 patients.

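### The drug-by-days (7 and 8) model in 2.7.1 cannot be run on the primary MSLT and FWL data, and relabelling the days leaves the primary FWL contrast, and so its power, open

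*Combined protocol and SAP*

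**What the plan says.** Section 2.7.1 gives one model for every in-lab sleep, sleepiness/fatigue and pain variable. These data "will be compared using two factor MANOVAs with drug (suvorexant vs placebo) and days (7 and 8) as the two repeated factors". The internet questionnaires have a sentence of their own and are not at issue.

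The schedule paragraph at the end of 2.4.2 puts PSG on nights 7 and 8. For the daytime tests it says: "During day 8 of each treatment a MSLT (1000, 1200, 1400, and 1600 hr) will be done, and on days 1 and 8"; the days 1 and 8 at the end of that extract are those of FWL testing. It adds: "On days 1 and 8 self-reported mood and pain indices will also be completed prior to each nociceptive sensitivity test".

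Section 2.7.1 itself lists, as primary daytime measures, the MSLT from day 8 and "the FWL test results (the average of the am and pm tests) from day 1 and day 8". It does not say how the two FWL days are combined.

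On the form of each measure, 2.5.2 says of the MSLT: "The latencies for the 4 tests are averaged to generate a single latency value". Section 2.5.3 says of FWL: "The primary dependent measure is mean FWL (to a resolution of 0.01 sec) for each of the 5 heat intensities".

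On power, 2.7.2 refers to Appendix A: "The sample sizes and associated powers are presented for each of the primary outcome measures". For FWL, Appendix A gives two paired t-test tables. Both use a difference of 2.6 s, with SD 2.5 in one and 3.5 in the other (the larger to allow for more variability in fibromyalgia). The effect comes from sleepy volunteers after 4 nights of sleep lengthened by 1 hr. Neither table names a study day.

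**The concern.** There is no day-7 value for MSLT or FWL, so the only model stated for the drug comparison cannot be fitted to either primary daytime endpoint. FWL carries the nociception objective and part of the second hypothesis in 2.1.2.

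Changing the FWL labels to days 1 and 8 makes the model estimable but does not say which of its tests is primary. At least three readings remain: the drug main effect over both days, the drug-by-day interaction, or day 8 alone. They estimate different quantities and have different power. If the choice stays open, it can be made after the data are seen.

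The meaning of day 1 is also open. The documents do not say whether day-1 testing comes before the first dose of the period. The nearest hint is in 2.5.5, on the safety scales: "Changes on any of these scales from the scores established at the baseline will be reported as AEs". That does not say whether the baseline is screening or day 1. If day 1 is before dosing, it is an untreated value and averaging it in halves the expected effect. If it is after, the result depends on a one-night effect that the documents do not give.

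**Working it through.** **1. Days in the model against days in the schedule**

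| Measure | Days in the 2.7.1 model | Days scheduled |
|---|---|---|
| PSG | 7 and 8 | 7 and 8 (2.4.2, 2.7.1); 8 and 9 (2.5.1) |
| MSLT | 7 and 8 | 8 only |
| FWL | 7 and 8 | 1 and 8 |
| In-lab pain ratings | 7 and 8 | 1 and 8 |
| In-lab sleepiness/fatigue ratings | 7 and 8 | no day given; the schedule names only mood and pain indices |

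**2. Appendix A reproduced.** Two-sided paired t-test, alpha 0.05, n=30, 29 df, noncentral t with noncentrality (difference/SD) x sqrt(n).

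- FWL, SD 3.5: 2.6/3.5 x sqrt(30) = 4.07, power 0.976 (stated 0.976).
- FWL, SD 2.5: 2.6/2.5 x sqrt(30) = 5.70, power 0.9998 (stated 1.000).
- MSLT, fibromyalgia table: 4.3/4.8 x sqrt(30) = 4.91, power 0.997 (stated 0.997).

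**3. MSLT.** There is one averaged value per test day and one test day per treatment. Without a days factor the model is the paired day-8 comparison, which is the form Appendix A powers. Only the wording is wrong.

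**4. FWL with days 1 and 8.** Three assumptions are needed, none of them in the documents: f, the day-1 effect as a share of the day-8 effect; r, the correlation between the day-1 and day-8 drug differences; and equal SDs of those differences on the two days.

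- Day 8 alone: difference 2.6, SD as in Appendix A.
- Two-day average: difference 2.6(1+f)/2, SD x sqrt((1+r)/2). In a two-by-two within-patient model the drug main effect is exactly the paired t-test on this average (checked on simulated data: F = t squared = 27.058).
- Drug-by-day interaction: difference 2.6(1-f), SD x sqrt(2(1-r)).

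Example for the average at SD 3.5, f=0, r=0.5: difference 1.3; SD 3.5 x sqrt(0.75) = 3.03; noncentrality 1.3/3.03 x sqrt(30) = 2.35; power 0.62. A simulation gave 0.627.

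Power of the two-day average, n=30:

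| SD | f | r=0 | r=0.5 | r=0.8 |
|---|---|---|---|---|
| 3.5 | 0 | 0.79 | 0.62 | 0.55 |
| 3.5 | 0.25 | 0.935 | 0.81 | 0.74 |
| 3.5 | 0.5 | 0.99 | 0.93 | 0.88 |
| 3.5 | 1 | 1.00 | 0.995 | 0.985 |
| 2.5 | 0 | 0.97 | 0.89 | 0.83 |
| 2.5 | 0.5 | 1.00 | 0.997 | 0.992 |

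**5. Break-even.** The average equals day 8 alone when (1+f)/2 = sqrt((1+r)/2), that is f = sqrt(2(1+r)) - 1. This gives 0.41, 0.73 and 0.90 at r = 0, 0.5 and 0.8.

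**6. Interaction at SD 3.5, r=0.5.** The SD is 3.5 x sqrt(1) = 3.5. At f=0 the difference is 2.6 and power is 0.976. At f=0.5 the difference is 1.3 and power is 0.50. The average moves the other way, from 0.62 to 0.93.

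**7. The equal-SD assumption.** At f=0, r=0.5 and a day-8 SD of 3.5, a day-1 SD of 0.7 or 1.3 times the day-8 SD changes the power of the average from 0.62 to 0.76 or 0.50.

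**The case against.** The best defence is that the days label is a slip, that the two-factor model is sound once it is corrected, and that nothing in the documents shows a loss of power. Much of this stands.

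- Any one of the three contrasts, named in advance, is a valid test. No type I error problem is claimed for such a contrast.
- f, r and the equality of SDs are all assumed. Under the SD 2.5 table, a half-size day-1 effect keeps the average at 0.99 or more for r up to 0.8.
- If day 1 is before dosing, the interaction from the same model has power 0.976 at r=0.5 (SD 3.5), where the average has 0.62.
- Day-1 FWL is listed among the primary measures, and the hypothesis concerns next-day nociception. Both sit more easily with testing after a dose, though they do not settle it.

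A reader might go further and infer that the two-day average is the plan's default FWL test, and that it has the Appendix A power only if day 1 carries an effect comparable to day 8. The documents do not support either step. Section 2.7.1 names no effect of the model as primary. The share of effect needed also depends on r and the SD: break-even is 0.41 at r=0, because averaging reduces variance as well as diluting the effect.

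The defence does not answer the mismatch itself, or the fact that the plan does not choose among contrasts that can give different answers.

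**Conclusion.** The plan is wrong as written and should be corrected. The stated model does not fit the MSLT or FWL schedule, and this needs no assumption to establish. For MSLT the consequence is wording only. For FWL the primary contrast is unspecified, and Appendix A's single paired difference does not identify it.

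The effect on power is conditional. At n=30 and SD 3.5, power can fall from 0.976 to between 0.55 and 0.79 for the two-day average with no day-1 effect (r from 0.8 to 0), or to 0.50 for the interaction with a half-size day-1 effect (r=0.5). At SD 2.5 the loss for the average is smaller (0.83 to 0.97 at f=0). If day 1 carries enough of the effect, averaging gains power. These figures rest on assumed f and r and on equal SDs. Appendix A's own arithmetic is correct.

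**What to change.** In 2.7.1:

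- (a) Limit the days (7 and 8) factor to the PSG measures, after reconciling the PSG nights (7 and 8 in 2.4.2 and 2.7.1; 8 and 9 in 2.5.1).
- (b) Analyse MSLT as the day-8 mean of the four tests, suvorexant versus placebo.
- (c) Name one primary FWL contrast before unblinding. One option is day-8 suvorexant versus placebo on the am/pm average, which has the single-difference form that Appendix A powers. This is a reviewer's preference; the documents do not dictate it. If the two-day average or the interaction is chosen, restate the FWL power for it with f, r and the SDs given.
- (d) State whether day-1 testing precedes the first dose of each period, since that decides whether day 1 is a period baseline or a treated value.
- (e) Reconcile the five intensity-specific FWL values in 2.5.3 with the single value in Appendix A, and give the correct days for the in-lab pain and sleepiness/fatigue ratings.

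The cost is a few lines in 2.5.1, 2.5.3 and 2.7.1, plus a revised FWL power table if day 8 alone is not chosen. No new data or patients are needed. If day 8 alone is chosen, day-1 FWL loses primary status. Should its effect equal that of day 8, a small gain is given up at SD 3.5: 0.976 instead of 0.985 to 1.00 for r from 0.8 to 0.

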2.3 Study Design

The study will be conducted as a double blind, placebo controlled, trial using a repeated measures design. Patients with fibromyalgia and co-morbid insomnia (n=30) will be treated for 9 nights each with suvorexant 20 mg and placebo with the order of treatments counterbalanced. The study will be registered on clinicaltrials.gov

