2.4 Study Flowchart

Patients with fibromyalgia and co morbid insomnia will be recruited from the HFHS hospitals and clinics and from patient support groups in Metro Detroit. In our most recent study of fibromyalgia we were able to recruit 20 patients over a period of twelve months. Patients will be assessed clinically for fibromyalgia and insomnia using American College of Rheumatology (ARC) (16) and Diagnostic and Statistical Manual of Mental Disorders (DSM-5) (17) criteria, respectively. They will be screened by PSG for other primary sleep disorders and a sleep efficiency (sleep time/bedtime) of < 85%.

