2.5 Study Procedures

2.5.1 Polysomnography (PSG)

For each PSG night, participants will arrive 2 hours prior to their reported bedtime to complete check-in procedures and undergo electrode placement for standard 8-hr PSGs (18). Bedtimes will be determined using the participant's self-reported normal sleep schedule with

time in bed fixed to 8 hrs. For the screening PSG, central and occipital electro-encephalogram (EEG) leads (C3-A2 and O2-A1) will be placed to measure EEG activity and left and right horizontal electroculograms (EOG) will be used to measure eye movements. A V5 electrocardiogram (ECG) lead and a sub-mental electromyogram (EMG) lead will be placed. Airflow (by pressure transducer), body position via video recording, thoracic and abdominal excursion (inductance plethysmography), oxygen saturation (finger pulse oximetry), leg movement (with electrode over left anterior tibialis muscle), and sound will also be recorded. For the study nights 8 and 9 the 8-hr PSGs will consist of continuous monitoring of two channels of EEG (C3-A2 and O2-A1), left and right EOGs, submental EMG and V5 ECG.

All recordings will be scored in 30 second epochs for standard sleep stages according to the standards of Rechtschaffen & Kales (18). Scoring will be done by technicians with established intra-laboratory scoring concordance and verified by review of the PI or Col. Respiratory events and periodic leg movement events will be scored according to established AASM published criteria (19). Based on the screening PSG, patients with respiratory or periodic leg movement event indices of > 10 will be excluded.

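### The crossover model in section 2.7.1 has no period term; adding one is a cheap precision gain of unknown size (minor)

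*Combined protocol and SAP*

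**What the plan says.** Section 2.3 has 30 patients "treated for 9 nights each with suvorexant 20 mg and placebo with the order of treatments counterbalanced". The schedule paragraph at the end of section 2.4.2 places this "in a cross over design with 7 nights of washout between treatments". That is a two-treatment, two-period crossover.

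Section 2.7.1 gives the only model for the in-lab endpoints: "two factor MANOVAs with drug (suvorexant vs placebo) and days (7 and 8) as the two repeated factors". It treats the internet questionnaire data in the same way, again with drug and days. Neither section 2.7.1 nor any other part of the document names period, order or sequence as a model term. Appendix A powers each primary measure with a paired t-test, which has no period adjustment either.

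The endpoints differ in how many values each period yields. For polysomnography (PSG), "The primary PSG efficacy variables will be sleep efficiency and WASO computed as a mean of nights 7 and 8", so sleep efficiency and WASO have one value per period, as does the Multiple Sleep Latency Test (MSLT) on day 8. Finger withdrawal latency (FWL) has two days per period: "the FWL test results (the average of the am and pm tests) from day 1 and day 8".

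**The concern.** In a two-period crossover, anything that changes between the first and second period (familiarity with the laboratory, practice at the heat test, drift in symptoms) enters every within-participant comparison. Participants who take suvorexant second have the shift added to their drug-minus-placebo difference; those who take it first have it subtracted. Counterbalancing removes this from the average difference but not from the spread of the differences. A model without period counts that spread as random error.

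What is at stake is precision: a wider confidence interval and a test with somewhat less power than it could have. WASO has the least room to lose, because among the primary measures it has the lowest planned power in Appendix A (0.837 or 0.692 at n = 30).

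**Working it through.** **Inputs.** n = 30 (sections 2.3 and 2.7.2). Two-sided alpha of 0.05, WASO effect 25 min with SD of the difference 45, and the alternative 20 min with SD 43 (Appendix A). Assumptions not in the documents: 15 participants per sequence; a fixed shift π of 5, 10 or 20 min; and, at first, planning SDs that do not already contain a shift.

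**Reproducing the plan.** Paired t-test power comes from the noncentral t with n − 1 = 29 df and noncentrality (δ/SD)√n. For 25/45 this gives 0.8367 (Appendix A: 0.837); for 20/43, 0.6924 (0.692). The planned figures reproduce.

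**Model.** The drug main effect in a drug-by-days repeated-measures analysis is the paired test on each participant's difference, averaged over days. With a shift, that difference is d = δ + π + e in one sequence and δ − π + e in the other.

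- *Without a period term:* the mean difference has bias π(n₁ − n₂)/n, which is 0 at 15/15. The sum of squares (n − 1)s²/SD² is noncentral chi-square with 29 df and noncentrality nπ²/SD², independent of the mean. Power is the probability that |T| exceeds t(0.975, 29) = 2.045, by numerical integration.
- *With a period term:* noncentral t with 28 df and standard error (SD/2)√(1/15 + 1/15) = SD/√30, whatever the shift.

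| WASO input | Without period, shift 5 / 10 / 20 min | With period |
|---|---|---|
| 25 min, SD 45 | 0.833 / 0.824 / 0.784 | 0.836 |
| 20 min, SD 43 | 0.687 / 0.673 / 0.615 | 0.691 |

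**Direction of the error.** With no drug effect and SD 45, type I error without the term is 0.045 at 10 min and 0.032 at 20 min, so below 0.05.

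**Interval width (SD 45).** Without the term, the typical SD of the differences is √(45² + π² × 30/29), or 46.1 at 10 min and 49.4 at 20 min. The 95% half-widths are 2.045 × 46.1/√30 = 17.2 min and 2.045 × 49.4/√30 = 18.4 min. With the term: 2.048 × 45/√30 = 16.8 min.

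**If SD 45 already contains the shift.** The residual SD is √(45² − π² × 30/29), or 43.8 at 10 min and 40.1 at 20 min. Power then goes from 0.843 without the term to 0.854 with it at 10 min, and from 0.862 to 0.909 at 20 min. All four exceed the planned 0.837.

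**Unequal completers.** Section 2.8 mentions 10% dropout, for drug supply only. Assume that it means 27 of 30 complete. A 14/13 split gives bias π/27: 0.4 min at a 10 min shift and 0.7 min at 20 min. The extreme, 15/12, gives 3π/27: 1.1 and 2.2 min. At 15/12, simulated type I error was still below 0.05 (0.046 at a shift of 0.25 SD, 0.035 at 0.5 SD).

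**Cost with no shift.** Moving from 29 to 28 df takes WASO power (25/45) from 0.8367 to 0.8357.

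**The case against.** The strongest reply is that no defect has been shown. Every power loss above rests on an assumed shift. At 5 or 10 min the loss for 25/45 is 0.003 or 0.012; only the 20 min shift, nearly as large as the 25 min drug effect, looks material. The plan also has features that should shrink a shift. Participants have a laboratory screening night before treatment ("They will be screened by PSG for other primary sleep disorders"), and the set-up for each PSG night is the same: "participants will arrive 2 hours prior to their reported bedtime to complete check-in procedures and undergo electrode placement for standard 8-hr PSGs". PSG outcomes are averaged over two nights late in each period. For FWL, "Patients initially will undergo a training session to familiarize themselves with the nociceptive testing equipment and procedures". All of this stands. It makes the point minor; it does not rule a shift out.

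A reader might go further and infer that the planned drug test is biased or invalid. The documents do not support that: order is counterbalanced, and at near balance the estimate is essentially unbiased with type I error at or below 0.05.

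The opposite over-reading, that the test is always conservative, also fails. No allocation method is given. If order were assigned by unconstrained randomisation, simulated type I error is about 0.05; with a marked imbalance such as 17/10 and a 0.5 SD shift, it is 0.065. Counterbalancing with 10% dropout does not lead there.

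A third inference would be that the planned analysis of two days per period ignores the correlation between days within a period. It does not: with drug and days both as repeated factors, drug is tested against its own between-period error, and simulated type I error was 0.050 at participant-by-period correlations of 0.1, 0.3 and 0.5.

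**Conclusion.** The point holds as a minor, inexpensive improvement. The stated model omits period, so any period shift stays in the error term. Given near-equal sequences, the planned test is valid but conservative and loses some precision. Unequal completers add a bias of shift × (n₁ − n₂)/n, which is small under 10% dropout.

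The size of the gain is unknown, because the documents give no shift and it may be zero. At 15 per sequence, with the planning SD free of the shift, the term recovers 0.012 of WASO power (25/45) at 10 min and 0.052 at 20 min; for 20/43 the figures are 0.018 and 0.076. It would be tempting to say that the trial has less power than Appendix A states. The documents do not settle that: if the planning SD already includes a shift, the stated power is not eroded and the term is a pure gain.

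**What to change.** In section 2.7.1, add period, with sequence as in the standard 2×2 crossover analysis, to the model for every in-lab endpoint and for the internet questionnaire data. Report the drug contrast with its 95% CI. Period does the work; in complete data the sequence term does not alter the drug contrast.

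- **One value per period** (sleep efficiency and WASO as two-night means, MSLT on day 8): use the standard 2×2 crossover ANOVA.
- **Days kept as a factor** (FWL, for whichever summary over heat intensities is analysed, and the questionnaires): keep day and drug-by-day, and test drug against between-period (participant-by-period) error. The planned repeated-measures test already does so. If a mixed model replaces it, include a random participant-by-period effect to preserve this.

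The cost is a short addition to section 2.7.1 and the one error degree of freedom costed above. It is best made before unblinding.

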2.1 Objectives and Hypotheses

2.1.1 The primary objectives of this proposed study in persons with fibromyalgia and comorbid insomnia are:

1) to assess the effect of suvorexant 20 mg versus placebo on polysomnographic (PSG) measures of sleep.

2) to assess the effect of suvorexant 20 mg versus placebo on next day measures of sleepiness/fatigue.

3) to assess the effect of suvorexant 20 mg versus placebo on next day measures of nociception and pain.

2.1.2 The clinical hypotheses to be tested are:

1) relative to placebo suvorexant 20 mg will increase PSG sleep efficiency and reduce sleep latency and wake after sleep onset in persons with fibromyalgia and comorbid insomnia.

2) relative to placebo suvorexant 20 mg will reduce self-reported next-day pain and nociceptive sensitivity as measured by Finger Withdrawal Testing (FWT) in persons with fibromyalgia and comorbid insomnia.

3) relative to placebo suvorexant 20 mg will reduce self-reported next-day fatigue and normalize Multiple Sleep Latency Test (MSLT) scores in persons with fibromyalgia and comorbid insomnia.

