2.5.4 Morning Self-reported Sleep and Previous Day Pain Assessment

Each morning after arising participants will complete a brief questionnaire regarding the previous night's sleep and the previous day's pain. The Red Cap questionnaires will be

accessed over the internet by participants' using their own password protected login identification credential with a daily time-limited completion interval (before 12 noon each day). The questionnaire will query regarding latency to fall asleep, wake time after falling asleep, total sleep time, pain disruption of sleep and alertness after awakening in the morning. Daytime pain the previous day will be assessed using the Short-Form McGill Pain Questionnaire (28).

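### The secondary diary analysis lists neither its days nor a missing-form rule: if all nine forms enter, some ratings are pre-dose, and MANOVA by default drops participants lacking an analysed form.

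*Combined protocol and SAP*

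**What the plan says.** Section 2.5.4 sets up a daily internet form: "Each morning after arising participants will complete a brief questionnaire regarding the previous night's sleep and the previous day's pain". The sleep items come first ("The questionnaire will query regarding latency to fall asleep, wake time after falling asleep, total sleep time"), and the previous day's pain is rated on the Short-Form McGill. Each form is open only for a limited time: "with a daily time-limited completion interval (before 12 noon each day").

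Section 2.3 places dosing at night. Participants "will be treated for 9 nights each with suvorexant 20 mg and placebo with the order of treatments counterbalanced".

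Section 2.7.1 makes the diary a secondary set: "morning ratings of sleep and previous day's pain collected on the internet administered questionnaires during each 9 day treatment condition". The in-lab MANOVAs just before use drug and "days (7 and 8) as the two repeated factors". The diary sentence follows: "The internet questionnaire data will be treated similarly using drug and days as two repeated measures". The levels of the diary's days factor are not listed. No section says when the first form falls relative to the first dose of a period, what happens to a rating of a pre-dose day or night, or how a missing form is handled.

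**The concern.** Two things are left to the analyst.

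The first is timing. A form completed after the first treated night rates pain from the day before that night, when no study drug of that period had been taken. Such a rating cannot show the drug's effect. If it is averaged into the drug comparison, it pulls the estimate toward no difference. A drug-by-days term could hint at this but would not correct the average.

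The second is completeness. The form closes at noon, so missed forms are foreseeable. Classical repeated-measures MANOVA needs every drug-by-day cell and, unless told otherwise, discards a participant who lacks one. That wastes usable forms in a sample of 30 and favours the more compliant participants.

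At stake are diary sleep and diary pain. The diary bears on the hypothesis in section 2.1 that the drug "will reduce self-reported next-day pain and nociceptive sensitivity", although the in-lab pain ratings address it too. A diluted or depleted diary result could be misread as no effect on reported pain.

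**Working it through.** **Reference figure.** The plan gives no power for the diary; Appendix A covers primary outcomes only. The power formula used here (two-sided paired t, noncentral t, n − 1 df, alpha 0.05) reproduces Appendix A: sleep efficiency, 8/12.8 = 0.625, n = 30, gives 0.911 as printed.

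**Pre-dose ratings per period, nine forms analysed.** Let night k follow day k, so that the first dose comes in the evening of day 1. The form on the morning of day c rates the daytime of day c − 1 and the night between.

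| Which nine forms | Pre-dose pain | Pre-dose sleep |
|---|---|---|
| (a) mornings after nights 1 to 9 | 1 | 0 |
| (b) mornings of days 1 to 9, day 1 before night 1 | 2 | 1 |

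The documents do not settle (a) or (b). Night numbering is itself loose: PSG nights are 7 and 8 in sections 2.4.2 and 2.7.1, but 8 and 9 in 2.5.1. If only days 7 and 8 are analysed, no rating is pre-dose.

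**Dilution.** Assume a constant effect from the first dose. The nine-day average keeps k/9 of it, where k is the number of post-dose ratings: pain loses 1/9 = 11% in (a) and 2/9 = 22% in (b); sleep loses 0% and 11%.

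For power, assume a standardised effect of 0.5 on the post-dose mean, n = 30, and between-day correlation r. The diluted effect is 0.5 × (k/9) × SD_k/SD_9, with SD_k = √[(1 + (k − 1)r)/k]. Undiluted power is 0.754.

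| k | r = 1 | r = 0.5 | r = 0 |
|---|---|---|---|
| 8 | 0.653 | 0.658 | 0.704 |
| 7 | 0.540 | 0.551 | 0.646 |

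**Complete participants.** A full set is 9 × 2 = 18 forms, or 2 × 2 = 4. With per-form completion q (assumed), the complete share is q^m for independent misses. For misses that cluster within people it is the beta-binomial probability of no miss, with intraclass correlation 0.3 (assumed). Expected participants kept, of 30:

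| q | 18 forms, independent | 18 forms, corr. 0.3 | 4 forms, independent | 4 forms, corr. 0.3 |
|---|---|---|---|---|
| 0.98 | 20.9 | 26.8 | 27.7 | 28.4 |
| 0.95 | 11.9 | 22.7 | 24.4 | 26.2 |

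For example, 0.95^18 = 0.397 and 30 × 0.397 = 11.9; 0.95^4 = 0.815 and 30 × 0.815 = 24.4.

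Power at an effect of 0.5 is 0.71 with 27 participants, 0.69 with 26, 0.65 with 24, 0.63 with 23 and 0.35 with 12.

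**All available forms at 95% completion.** All 30 stay in. In the worst case (r = 0) the effect becomes 0.5 × √[(1/D)/E(1/m)], where D is the number of days and m the number of forms present. For nine days E(1/m) = 0.1177, the effect is 0.486 and power is 0.73. For two days E(1/m) = 0.5476, the effect is 0.478 and power is 0.72. With r = 1, power stays at 0.75.

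**The case against.** The strongest reply is that the diary sentence directly follows the one naming days 7 and 8 and says the data are treated similarly. If that carries the days over, the pre-dose problem disappears. This stands as far as it goes: the nine-day reading is open, because the preceding text describes collection over the whole condition, but it is not established. A reader might infer that the plan does average pre-dose ratings into the drug effect. The documents do not say so.

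A reader might also infer that the plan excludes anyone with a missed form. It does not. It is silent, and the exclusion is the usual default of the method named. On the days 7 and 8 reading only the four analysed forms matter; a participant who misses any other form is kept.

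The magnitudes are assumed throughout. Keeping 12 of 30 takes the nine-day reading, 95% completion and independent misses together. Misses usually cluster within people, and with correlation 0.3 the loss is much smaller. The 22% dilution needs case (b) as well as a constant effect. The plan claims no power for the diary.

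Finally, a mixed model is not the only remedy. Period means over the available forms are also valid. All of this lowers the weight of the point. It does not supply the missing days or the missing-form rule.

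**Conclusion.** The point holds as a minor one. Section 2.7.1 leaves open which diary days enter, and no section gives a rule for pre-dose ratings or missing forms.

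- On the nine-day reading at least one pain rating per period is pre-dose, and the averaged pain effect shrinks by 11% or 22% under a constant effect. On the days 7 and 8 reading there is no dilution.
- If the MANOVA runs with its usual default, the loss of participants ranges from slight (about 28 of 30 kept: 4 forms, 98% completion) to severe (about 12 of 30: 18 forms, 95% completion, independent misses).

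These sizes rest on assumed completion, effect size and correlations, none of which the documents give. PSG, MSLT, finger withdrawal latency and the sample size of 30 are untouched, so a large loss or a threat to the trial's main conclusions should not be read into this.

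**What to change.** In section 2.7.1:

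1. List the diary days in the drug comparison and say when the first form falls relative to the first dose of each period. Assign each pain rating to the day, and each sleep rating to the night, that it describes. Leave pre-dose ratings out of the drug contrast, or use them as that period's baseline.
2. Analyse all available forms with a linear mixed model: fixed drug, period, sequence, day and drug-by-day; random participant and participant-by-period; and a small-sample degrees-of-freedom correction such as Kenward-Roger. Make the drug effect averaged over post-dose days the main contrast. A simpler acceptable alternative is a paired analysis of each participant's period means over available post-dose forms, allowing for period.

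The participant-by-period term should not be left out of the mixed model. In simulation (n = 30, nine days, 8,000 runs), a model with random participant only had type I error of 0.158 and 0.249 when participant-by-period variance was 10% and 20% of within-participant variance. A paired t on period means held 0.046 to 0.055. This is a caution about the replacement model, not evidence against the plan's MANOVA.

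The cost is wording only: no new data, visits or forms. The downside is reliance on missing at random and, for the mixed model, on a chosen covariance structure. Both should be stated.
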